Fatty acid supplementation will continue until the baby is full term (40 adjusted weeks of age). If the infant is discharged before he/she is full-term, the infant will be sent home with a bottle of the fatty acid oral solution for the infant to continue daily until he/she is full-term (40 weeks of age). The infant's nutritional needs will be carefully monitored by his/her doctor and nutritionist per NICU protocols.

To monitor the amount of fatty acid nutrition getting into the blood, we will check the infant's blood. As much as possible, we will coordinate the study blood collection at the same time as the routine NICU blood draws. We will collect 1.3 milliliters of blood at 4 different times spread apart while the infant is in the hospital. At each time point, we will collect about 1/4 teaspoon of blood, for a total of about 1 teaspoonful.

The blood draws will occur as the following four time points:

- Blood draw T0= Prior to parenteral nutrition, within 1st 3 days of life. This blood collection should be

taken from cord blood. If cord blood is not available, sample will be collected from a UAC, UVC, or peripheral blood draw concurrent with SOC.

- Blood draw T1= 5 days after parenteral nutrition is started; grace period +/-3 days therefore total 2-8 days after parenteral nutrition started.
- Blood draw T2= 5 days after enteral nutrition full feeds have arrived; grace period +/-3 days therefore total 2-8 days after full enteral nutrition arrived.
- Blood draw T3= Prior to discharge from hospital coinciding with time that ROP may be present, ≥ 35 weeks adjusted age.

This blood will be used for looking at what new genes (mRNA) the infant is making and to check how many and what kind of fatty acids the infant has in the blood. Before testing, the blood will be stored in a storage facility at the UCSD Department of Ophthalmology Blood Bank and labelled with a barcode without the infants' personal information. This is not the infant's DNA, and no DNA will be isolated or tested. Samples will be stored for 10 years. After this time point, all samples will be destroyed if not used by that time. If the parent decides to withdraw consent the blood samples that were already drawn will be destroyed, however, any previously obtained data from sample testing will be kept.

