Eye exams: All infants will get eye exams according to standard NICU protocols. Serial eye exams will be performed according to the usual intervals, which is until retinal vascularization has matured or active ROP has stabilized, usually at 1-2 months post-term. The area of vascularized retina, clock hours of neovascularization, and amount of retinal vascular dilation and tortuosity will be measured by indirect ophthalmoscopy in all infants at each clinical exam by an ophthalmologist masked to the treatment group. Stage of retinopathy of prematurity and need for ROP treatments will be measured at 40 weeks gestation plus or minus three weeks and followed over time. Infants with ROP will be monitored over time for longer term visual and anatomic outcomes. For both groups, infants will have SOC eye examinations prior to discharge around 40 weeks GA (≥ 38 wks GA). For both groups, if infant is discharged prior to 38 weeks GA, we will collect follow-up data from their outpatient follow-up eye exam from UCSD or other provider

Nutrition: Omegaven has been approved by the FDA for use in children and infants with parenteral nutrition associated liver disease (PNALD). In this study we intend to use Omegaven under an IND exemption to study the use of the drug in reducing the incidence and severity of retinopathy of prematurity (ROP). Our aim is to differentiate the phospholipid profiles and gene expression pathways of at-risk very low birth weight infants with and without treatment with Omegaven® (high n-3 fish oil supplement) and to establish whether omega-3 fatty acid supplementation in extremely low birth weight infants will reduce the incidence and severity of retinopathy of prematurity (ROP). The study intervention “drug product” has been used in the neonatal population via the same route of administration safely for other disease indications internationally and nationally including here at University of California San Diego. This investigation does not significantly increase the risk or decrease the acceptability of risk of our study population.

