Once enteral nutrition reaches desired minimum mL/kg/day (determined by the NICU neonatology team), then parenteral supplementation will be discontinued and enteral supplementation will begin. Carlson’s Fish oil ® (400 mg of omega 3 fatty acids: EPA 200 mg, DHA 125 mg, and 75 mg of other omega-3 fatty acids per ¼ tsp) will be given in the experimental group. Enteral fish oil supplementation of 1.25mL/kg/day (1/4 teaspoon per kg per day) divided at least every 12 hours for tolerance will be continued until the baby is at 40 weeks adjusted age or the retina is fully vascularized. We will adjust our fish oil dosage to maintain maximum enteral DHA supplementation to 125 mg/kg/day (omega3 400mg/kg/day). The total dose will be given BID initially. If there are any symptoms of GERD or other intolerance symptoms that are concerning to the primary team, then oral fish oil total daily dose will be divided over multiple administrations. If enteral oil is not tolerated even after medical management, we can decrease the amount by 25% until tolerated. We do not expect poor tolerance to this dose given 120 mg/kg/day has been tolerated as an emulsion via feeding tube without any complications²¹. As it is typical of this study population to require varying needs of care and drug administration, should any infant randomized to the Omegaven arm require discontinuation of the study drug for clinical reasons for more than

five days (either consecutive or accumulative), that infant will be withdrawn from the study. Drug administration disruptions occurring for 5 or less days (total) shall not be considered protocol deviations but will be recorded and noted in the annual FDA safety report.

Following discharge from the NICU and prior to infants reaching 40 wks, a research team member (other than the PI) will contact the parents with infants in the Omegaven arm once weekly to encourage parents to continue with the prescribe fish oil administration for their infant until he/she has is 40 weeks adjusted age.

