The investigational drug pharmacy (IDS) will obtain the Omegaven and dispense it to the nurse for administration in a separate line than the rest of the nutrition (amino acids, sugars, etc). The NICU nutritionist will optimize the total nutritional calories to the infant per NICU protocols. The IDS pharmacist, nutritionist, and NICU team will not be blinded to ensure that the infant in the Omegaven group meets all the nutritional requirements as determined by the NICU neonatology attendings and fellows involved in the study. The ophthalmology team will be blinded to the treatment group to prevent any potential for bias during the eye exam.

Outcome Measures:

Outcome 1: Change in concentrations of basic fatty acids (EPA, DHA, and AA) and their bioactive metabolites will be assessed at multiple time points.

Outcome 2: Change in mRNA expression of TNF- α , PPAR- γ , and VEGF at multiple time points.

Outcome 3: Severity stage of ROP in Group 1 compared to Group 2. This will be assessed at the time of ROP screening (approximately 31 weeks), and the outcome will be measured at approximately 40 weeks adjusted age. The stage of ROP at 40 weeks adjusted will be used for statistical analyses.

Safety:

A data safety monitoring board (DSMB) will be established to monitor the safety of enrolled infants in the study as well as identifying the efficacy of the treatment at ongoing intervals. The DSMB will meet after the first 5 infants are enrolled and then regularly at multiple intervals during the study. Clinical safety assessments will occur during the hospital admission including vital signs, weight, physical exam and laboratory assessments of triglycerides. The neonatologist will review the assessments and determine if the subject should remain in the study or be removed.

Statistical Analysis

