Our primary analytic approach will use generalized linear mixed models (GLMM). These methods will address problems of missing data, variable timing of the subject visits, and other possible unintended violations of design. Although our retention and follow-up plan is designed to minimize missing data, an advantage of the GLM models is that they allow us to maximize statistical power by not excluding subjects with some missing data. More specifically, GLM assumes that the data can be missing at random (MAR) or missing completely at random (MCAR). The benefit of this assumption is with a repeated measure problem (e.g., longitudinal data) you can still analyze data from all subjects, even if some have missing data (assumed MAR or MCAR). Mixed regressions will also allow us to estimate an intercept and slope for each patient based on all available data for that individual augmented by the data from the entire sample, with two random effects being used to model time trends (i.e., a random intercept and a linear trend). Further details of selected analyses related to each outcome are provided next.

For Outcome (a-b), the primary outcome is DHA at a specified period of time (i.e. 40 weeks) to assess the basic fatty acids. Outcome (a) posits that patients in Group 1 will differ from those in Group 2 with respect to i) DHA

ii) EPA iii) AA iv) bioactive metabolites. To assess Outcome (a) (i.e. to evaluate the effects of group, time, and their interaction on the change from baseline DHA measurements), a mixed effects model with group (IV Omegaven then PO baby fish oil or Intralipid), time, and group by time interaction as fixed effects, and random intercept and slope to account for within subject correlation. We expect that the interaction in question will be significant.

For Outcome (c), we hypothesize that Group 1 and Group 2 will have a different severity stage of ROP. To assess Outcome (c), we will use a *Mixed-effects ordinal logistic regression model* with severity stage of ROP after 40 weeks (Stage I, II, III, IV, V) as the outcome variable. The same fixed and random effects mentioned above will be used in evaluating Outcome(c).

All statistical analyses will be performed using SAS software version 9.3 (SAS Institute, Cary, North Carolina, USA).

[figure not shown]
Power Calculations

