10. HUMAN SUBJECTS

The University of California, San Diego (UCSD) is the only site participating in this study.

We anticipate enrolling 60 infants and up to 60 mothers at UCSD. We will consider patients for enrollment into this study for 5 years.

INFANT:

Inclusion Criteria:

- Infants born \geq 23 weeks gestation and \leq 30 weeks gestation or less than 1500 g at birth.
- Infant whose parent or guardian signed the written consent and HIPAA form.

Exclusion Criteria:

- Patients with liver disease attributable to known causes (i.e. genetic disease, hepatitis) and/or bleeding or clotting abnormalities will be excluded as shown by LFTs.
- Infants $<$ 23 weeks gestation

MOTHER:

- Any mother 18 years of age or older that allows their infant to be enrolled.
- Proficiently English speaking/reading and can complete questionnaire

Infants may still be enrolled in this study if the mother declines to be also participate in the study.

Participation in research is entirely voluntary. Parents of subject may refuse to participate or withdraw at any time without penalty or loss of benefits to which they are entitled. If the parent of subject decides that he/she no longer wishes to continue in this study, the subject's parents will be required to notify the study doctors, [name] or her research staff by calling her at [contact].

The study doctor may decide to take the subject off of the study without the parent's consent if:

- Subject is unable to meet the requirements of the study;
- Subject's medical condition changes;
- New information becomes available that indicates that participation in this study is not in the subject's best interest;
- If the study is stopped,
- The sponsor of the study or the competent authority has the right to withdraw the subject from the study without the parent's permission,
- The study physician can withdraw the subject from the study without the parent's consent if he/she comes to the conclusion that further participation is not in subject's best interest. This can be due to disease or side effects or because subject does not comply with study procedures

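### Omegaven infants off study drug for more than five days must leave the study itself; controls have no such rule and no analysis set is defined, so the DHA and ROP comparisons may be biased

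*Combined protocol and SAP*

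**What the plan says.** The rule is in section 9, Nutrition: "should any infant randomized to the Omegaven arm require discontinuation of the study drug for clinical reasons for more than" five days, whether in one stretch or added up, "that infant will be withdrawn from the study". Interruptions of five days or less in total are recorded and go into the annual FDA safety report. For longer ones the text gives only the withdrawal.

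Other provisions that bear on this:

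- **Blinding (section 9, Nutrition).** "The IDS pharmacist, nutritionist, and NICU team will not be blinded"; only the ophthalmology team is.
- **Discretionary removal in either arm.** Section 9, Safety: "The neonatologist will review the assessments and determine if the subject should remain in the study or be removed". Section 10 lets the study doctor take an infant off study for several reasons, including that the infant's "medical condition changes".
- **Data retention (section 9, Laboratory blood draws).** If a parent withdraws consent, "any previously obtained data from sample testing will be kept". The five-day rule has no equivalent sentence.
- **Eye examinations (section 9, Eye exams).** "All infants will get eye exams according to standard NICU protocols".
- **Analysis (section 9, Statistical Analysis).** Mixed models are chosen because "they allow us to maximize statistical power by not excluding subjects with some missing data", under MAR or MCAR. The fixed effects are group, time and their interaction.
- **Sample size (section 9, Power Calculations).** About 60 are enrolled so that 40 complete treatment.

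No section names an intention-to-treat, per-protocol or other analysis set.

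**The concern.** The rule operates after randomisation, is mandatory, and ends participation rather than dosing alone. Controls receive no study product, so they cannot trigger it. Infants who cannot stay on the product for clinical reasons may well be sicker, and section 7 itself links severe lung disease and oxygen exposure to retinal damage. Removing such infants from one arm only would leave a healthier Omegaven group beside an unselected control group. Masked eye examiners protect the grading of ROP but not the choice of who is graded.

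Withdrawn infants also received less product. Leaving them out answers a question about infants who tolerated Omegaven, whereas randomisation supports a comparison of the assigned strategies. Safety follow-up may also be cut short in the infants who could not stay on the product.

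**Working it through.** **1. The plan's own figures.** From section 9, Power Calculations: 20 per arm, mean DHA changes 42 and 27 µmol/L (difference 15), SD 15, two-sided 0.05. The noncentrality is 15 / (15·√(1/20 + 1/20)) = 3.16 with 38 df, giving power of 86.9% (88.5% by the normal approximation). This agrees with the stated figure of over 80%. Enrolment: 40 / (1 − 1/3) = 60, so the plan allows for 20 of 60 (33%) not completing, not split by arm or reason. The sizing arithmetic is sound.

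**2. What is available after a five-day withdrawal.**

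- *DHA:* samples taken before withdrawal can enter the mixed model. Later T1–T3 samples are not provided for. Under MAR with no illness covariate, the model in effect carries the infant along the on-drug trend.
- *ROP:* the analysed outcome is stage at about 40 weeks. A clinical eye examination will usually exist, but nothing commits the study to using it for a withdrawn infant. A model cannot supply a stage that was not collected.

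**3. Illustration of selection bias (assumed inputs).** Assume no true effect, no controls lost and nothing used after withdrawal. Withdrawal propensity and outcome are bivariate normal with correlation ρ, and the top fraction p of the Omegaven arm is removed. The values of p and ρ, and the direction of the association, are assumptions. The top value, p = 33%, borrows the plan's overall non-completion figure. The event rate is 22/70 = 31.4%, the control-arm laser rate of the trial cited in section 7, which is not this trial's ordinal endpoint.

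- Retained event rate = P(event and retained) / (1 − p).
- DHA shift = ρ × 15 × φ(z) / (1 − p), with z the upper-p normal quantile. Example for p = 0.20, ρ = 0.5: z = 0.842, φ(z) = 0.280, so 0.5 × 15 × 0.280 / 0.80 = 2.62.
- False-positive rate: 40,000 simulated trials, two-sided t-test, 27, 24 or 20 retained against 30 controls.

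| ρ | p | Event rate, retained Omegaven | DHA shift, µmol/L (% of 15) | False-positive rate |
|---|---|---|---|---|
| 0 | any | 31.4% | 0 | about 5.0% |
| 0.3 | 10% | 29.2% | 0.88 (6%) | 5.4% |
| 0.3 | 20% | 27.5% | 1.57 (10%) | 6.6% |
| 0.3 | 33% | 25.4% | 2.45 (16%) | 8.4% |
| 0.5 | 10% | 27.5% | 1.46 (10%) | 6.5% |
| 0.5 | 20% | 24.4% | 2.62 (17%) | 9.8% |
| 0.5 | 33% | 20.9% | 4.09 (27%) | 15.6% |

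**4. The same point by relative risk.** If withdrawn infants have k times the risk of those retained, the retained risk is 31.4% / (1 − p + pk). For k = 2 this is 28.6%, 26.2% and 23.6% at p = 10%, 20% and 33%, a spurious risk ratio of 0.91, 0.83 and 0.75. At k = 1 there is no bias.

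**5. Treatment effect in all randomised infants.** If withdrawn infants would show the control-level DHA change, the all-randomised difference is 15(1 − p) = 13.5, 12 or 10. A retained-only analysis that still shows 15 overstates it by 1.5, 3 or 5 µmol/L.

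**The case against.** The strongest points on the other side are these.

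- *The 33% column is extreme.* The plan's 33% covers both arms and all causes, and its 40 completers are split equally. With 20 of 30 kept in both arms under the same selection, the false-positive rate is about 5.3% (ρ = 0.3) or 6.1% (ρ = 0.5), against 8.4% and 15.6%. This stands: the 33% rows are an upper corner of the illustration. The plan has no by-arm figure to replace them.
- *The t-test is only the sizing method.* The planned mixed model uses earlier samples, so the simulated rates are not estimates for the primary test. This also stands, but the model's protection rests on MAR without illness covariates and does not help an uncollected 40-week ROP stage.
- *Correlation and direction are assumed, and the effect may be small.* True. No passage links stopping the product to DHA or ROP. The largest DHA shift, 4.09, is below one standard error of a 20 versus 30 comparison: 15·√(1/20 + 1/30) = 4.33.
- *Withdrawals may be few.* The plan divides or reduces the enteral dose before stopping and does not expect poor tolerance. That may lower the frequency in the enteral phase; the documents give no rate.
- *A matching control rule is impossible.* Agreed, so the remedy does not ask for one.
- *Eye data and safety oversight already exist.* Standard examinations cover all infants and the DSMB covers enrolled infants. This makes the fix cheap. It does not say that a withdrawn infant's later results are used.
- *A clinical-team opt-out can itself be informative.* Correct, so opt-outs need recording by arm and reason.

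**Conclusion.** The concern holds and should be fixed before the analysis is relied on. The documents establish mandatory study withdrawal in one arm only, a clinical trigger applied by unblinded staff, no defined analysis set, and no stated use of later outcomes. What they do not establish is how many infants are affected or how withdrawal relates to outcome, so the size of the bias is unknown and may be zero.

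If withdrawn infants have worse prognosis, the bias probably favours Omegaven. At 10% to 20% withdrawn, the illustration gives a spurious fall in event rate from 31.4% to between 29.2% and 24.4%, and a DHA shift of 0.9 to 2.6 µmol/L. At 33% in one arm it reaches 20.9% and 4.1 µmol/L. The point is serious because outcomes that were never collected cannot reliably be recovered at analysis.

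**What to change.** **Section 9, Nutrition.** Separate stopping study drug from leaving the study, leaving the rule on when drug is stopped as it is. Unless the parent withdraws consent or the clinical team objects, keep collecting the scheduled T1–T3 samples, the standard-of-care eye results and safety data. Record every opt-out by arm and reason.

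**Section 9, Statistical Analysis.** Make the primary DHA and ROP analyses include all randomised infants in their assigned arm. Add treatment completers and a missing-not-at-random analysis as sensitivity analyses. State how deaths and missing 40-week outcomes are handled, and report withdrawals and deaths by arm and reason.

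**Section 9, Power Calculations.** State that the 40 completers are a sizing figure and not the analysis set.

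**Cost.** Wording and follow-up of withdrawn infants, with no extra infants or visits. The remaining 1.3 mL draws are research samples carrying the anaemia risk described in section 14, which is why the clinical team needs an opt-out.

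The DHA difference is diluted. With all 60 infants contributing (30 per arm, SD 15) and withdrawn infants responding like controls:

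| Omegaven infants withdrawn | Difference | Power, SD 15 | Power with mixture variance, 225 + p(1 − p)·225 in that arm |
|---|---|---|---|
| 10% | 13.5 | 92.9% | 91.8% |
| 20% | 12 | 86.1% | 83.4% |
| 33% | 10 | 71.9% | 67.3% |

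The planned 20 per arm gives 86.9%. Power therefore stays above 80% up to 20% withdrawn and falls below it at 33%. If only 20 per arm supplied a DHA outcome, the mixture-variance figures would be 77%, 66% and 50%, so complete follow-up matters.

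### Omegaven infants off study drug for more than five days for clinical reasons leave the study itself, so later safety, blood and 40-week ROP data can be lost in one arm only

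*Combined protocol and SAP*

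**What the plan says.** The rule is in section 9, under Nutrition. It begins "should any infant randomized to the Omegaven arm require discontinuation of the study drug for clinical reasons for more than" and continues "five days (either consecutive or accumulative), that infant will be withdrawn from the study". Shorter gaps are treated differently and go into the yearly safety report to the FDA: "Drug administration disruptions occurring for 5 or less days (total) shall not be considered protocol deviations but will be recorded and noted". No such sentence covers the longer stops.

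Other text in section 9 that bears on this:

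- **Blood draws.** There are four, T0 to T3. The last is described as "Blood draw T3= Prior to discharge from hospital coinciding with time that ROP may be present". The only text on samples and data after a withdrawal concerns parents: "If the parent decides to withdraw consent the blood samples that were already drawn will be destroyed", while results already obtained are kept.
- **Eye exams.** All infants have standard-of-care exams. For infants of either group discharged before 38 weeks, "we will collect follow-up data from their outpatient follow-up eye exam from UCSD or other provider".
- **Outcome Measures.** For ROP, "The stage of ROP at 40 weeks adjusted will be used for statistical analyses".
- **Safety.** "The neonatologist will review the assessments and determine if the subject should remain in the study or be removed". This discretionary removal, like those listed in section 10, can reach either arm.
- **Statistical Analysis.** The mixed models keep subjects with partial data and assume data missing at random (MAR) or completely at random. A retention and follow-up plan is mentioned, but the available text does not set it out.
- **Power Calculations.** 60 infants are enrolled to obtain 40 who complete treatment.

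**The concern.** The rule makes no distinction between stopping a treatment and leaving the trial. It is mandatory, it names one arm, and it is triggered by clinical course after randomisation. Treatment runs from the first week of life to 40 weeks adjusted age, so exposure to the rule is long. The available text defines no status of off drug but still on study, and no intention-to-treat set.

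Three things are at stake:

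- **Safety.** Events after a long clinical stop are among the most informative, and they may go unrecorded.
- **ROP.** A single late value is analysed, so an infant withdrawn before 40 weeks may contribute nothing. The arms compared would then no longer be the arms randomised.
- **DHA.** Values taken before withdrawal stay in the model, but the later ones, at or near the 40-week primary time point, may be missing for infants whose exposure has changed.

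**Working it through.** **1. The plan's own figures.** Power Calculations gives mean changes of 42 and 27 µmol/L (difference 15), a largest SD of 15, 20 per arm and two-sided alpha 0.05. A two-sample t-test (noncentral t) gives 86.9%, which agrees with the stated power of over 80%. Enrolment of 60 for 40 completers allows (60 - 40)/60 = 33% non-completion for any reason. That is 10 of 30 per arm if split equally, and it is only a loose upper bound on withdrawals under this rule.

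**2. Which draws are at risk.** T1 is due 5 days after parenteral nutrition starts, with a window of 2 to 8 days. The rule needs more than 5 days off drug. Withdrawal before T1 would require the drug to be off almost from the start and T1 to fall late in its window. T0 and T1 will therefore nearly always exist. The loss is normally T2 and T3, or T3 alone.

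**3. What the mixed model does for DHA.** The infant's T0 and T1 values are used. Under MAR, with a group-by-time term and a random slope, the model in effect continues that infant on a path informed by its own on-drug values and by the Omegaven infants still observed. An infant who has stopped the drug need not follow that path. MAR is also doubtful where leaving depends on clinical problems that are not in the model.

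**4. Illustration for ROP.** Assumptions: no true effect; risk p = 22/70 = 31.4% in both arms (the control laser rate that section 7 reports from the cited Polish study, standing in for stage); 30 per arm; k Omegaven infants withdrawn; their risk is m times p.

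Rate among those retained = (30p - k·m·p)/(30 - k)

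| k | m = 0.5 | m = 1 | m = 2 |
|---|---|---|---|
| 3 | 33.2% (+1.7) | 31.4% (0) | 27.9% (-3.5) |
| 6 | 35.4% (+3.9) | 31.4% (0) | 23.6% (-7.9) |

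Shifts are in percentage points. For scale, the difference in the cited study is 22/70 - 9/60 = 31.4% - 15.0% = 16.4 points.

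**5. Power cost of keeping these infants.** Take 30 per arm, difference 15, SD 15, and 3 off-drug infants who keep none of the effect.

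- Dropped (27 v 30): t-test power 95.9%.
- Kept (30 v 30): mean difference 15 × 27/30 = 13.5. At SD 15, power is 92.9%. Mixing on-drug and off-drug infants raises the Omegaven SD to √(225 + 15² × 0.1 × 0.9) = 15.7, and simulation with that mixture gives about 92%.

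Both exceed the 86.9% in step 1.

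**The case against.** The strongest reply is that the plan never says observation stops. All infants get standard-of-care eye exams, outside exam data are collected for both groups, the DSMB remit covers enrolled infants, and the consent form and retention plan are not available. So much of the information may still be in the chart. This stands as far as it goes: a reader might infer that the plan orders these data to be discarded, and it does not. But no text says that the study uses those exams, or records later events, for an infant it has withdrawn.

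A reader might also infer that withdrawn infants vanish from the DHA analysis, so that the comparison rests only on infants who stayed on drug. The documents do not support that. The Statistical Analysis section keeps subjects with partial data, and these infants will nearly always have T0 and T1. What remains is the weaker point about MAR in step 3.

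The likelihood of withdrawal is not shown either. The protocol splits doses and reduces them by 25% before stopping enteral oil, tolerates up to five days off drug, and expects good tolerance. The ROP illustration uses laser need rather than stage, its inputs are assumed, and its range spans zero. With 30 per arm at 31.4%, the standard error of a difference is √(2 × 0.314 × 0.686/30), about 12 points, so every shift shown is under one standard error. All of this limits the size that can be claimed. It does not make a one-sided withdrawal rule sound.

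**Conclusion.** The concern holds. The plan states a mandatory rule, for the Omegaven arm only, that takes infants out of the study when only the drug needs to stop, and nothing available repairs it. Later safety data, T2 or T3, and the 40-week ROP stage can be lost selectively in that arm.

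Neither direction nor size of bias can be fixed from the documents. It is tempting to conclude that the rule flatters Omegaven, but clinical reasons are not limited to drug reactions or to infants at higher ROP risk. If withdrawn infants are at average risk the ROP shift is zero, and if they are at lower risk Omegaven looks worse. The shifts of +3.9 to -7.9 points rest on the assumptions in step 4, with up to 6 of 30 withdrawn. Nor is the planned power figure wrong: it reproduces. The problem is possible bias and lost safety follow-up. The change should be made; the number of infants affected is the main unknown.

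**What to change.** In section 9 (Nutrition), replace withdrawal from the study with discontinuation of study drug. Add that, unless the parent withdraws consent, the infant stays in the study and is analysed in the randomised group, with:

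1. in-hospital safety data taken from the chart;
2. the standard-of-care ROP outcome at about 40 weeks, as already described under Eye exams;
3. the remaining scheduled draws, where the clinical team finds them acceptable.

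Include stops of more than five days in the annual FDA safety report alongside the shorter ones. Clinical decisions to stop the drug do not change.

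The cost is a short protocol and IRB amendment (with matching consent wording if it is not already there), slightly more chart abstraction, and a diluted DHA contrast. No visits are added, and no draws beyond the four planned. On the basis in step 5, the dilution costs about 4 points of power (about 96% to about 92%).
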